5 SUBJECT INCLUSION AND EXCLUSION CRITERIA

5.1 Subject Inclusion Criteria

1. Males or females \geq 18 years of age
2. Subject-reported DLD (likely subjects with a history of multifocal IOLs, post-laser-assisted in situ keratomileusis [LASIK], corneal scars, and keratoconus)
3. Ability to comply with all protocol-mandated procedures independently and to attend all scheduled office visits
4. Otherwise healthy and well-controlled subjects
5. Able and willing to give written consent to participate in this study
6. Able to self-administer study medication
7. [REDACTED]
8. \leq 30 Early Treatment Diabetic Retinopathy Study (ETDRS) letters (20/63 Snellen or worse) in mLCVA score in at least one eye using the [REDACTED]
9. [REDACTED]

5.2 Subject Exclusion Criteria

Excluded from the study will be individuals with the following characteristics:

Ophthalmic (in either eye):

1. Prior unresolved dry eye diagnosis, taking prescription drops for dry eye, or taking artificial tear drops routinely for dry eye
2. Prior history of fluctuating vision
3. Clinically significant ocular disease as deemed by the Investigator (e.g., untreated cataract, glaucoma, corneal edema, uveitis, severe keratoconjunctivitis sicca, retina degeneration, loss of visual field due to glaucoma or stroke, branch retinal vein occlusion, retina flare) that might interfere with the study
4. Known hypersensitivity to any topical alpha-adrenoceptor antagonists
5. Known allergy or contraindication to any component of the vehicle formulation
6. History of cauterization of the punctum or punctal plug (silicone or collagen) insertion or removal
7. Ocular trauma, ocular surgery (e.g., IOLs), or laser procedure (e.g., LASIK, photorefractive keratectomy [PRK]) within 6 months prior to screening

8. Use of any topical prescription or over-the-counter (OTC) ophthalmic medications of any kind (including artificial tear drops) within 7 days of screening until study completion, with the exception of lid scrubs with OTC products (e.g., OCuSOFT® lid scrub, SteriLid®, baby shampoo, etc.)
9. Recent or current evidence of ocular infection or inflammation in either eye (such as current evidence of clinically significant blepharitis, conjunctivitis, or a history of herpes simplex or herpes zoster keratitis at screening in either eye). Subjects must be symptom free for at least 7 days.
10. History of diabetic retinopathy, diabetic macular edema, or dry or wet macular degeneration
11. History of any traumatic (surgical or nonsurgical) or non-traumatic condition affecting the pupil or iris (e.g., irregularly shaped pupil, neurogenic pupil disorder, iris atrophy, iridotomies, iridectomy, etc.)
12. Unwilling or unable to discontinue use of contact lenses on their scheduled visits at least 1 hour for soft contact lenses and at least 8 hours for hard gas-permeable contact lenses before ophthalmic assessments at screening, and at least 8 hours (for both types of lenses) before Day 8 and Day 15
13. People with undiagnosed dry eye, at the determination of the Investigator. Dry eye evaluation should be based on one of the following dry eye tests:
 - a. TearLabs osmolarity test (> 308 mOsm/L in either eye or an inter-eye difference ≥ 10 mOsm/L)
 - b. Corneal fluorescein staining (\geq grade 2 in the inferior or \geq grade 1 in the central zone using the National Eye Institute scale)
 - c. Tear break-up time of < 5 seconds

Systemic:

1. Known hypersensitivity or contraindication to alpha- and/or beta-adrenoceptor antagonists (e.g., chronic obstructive pulmonary disease or bronchial asthma; abnormally low BP or HR; second- or third-degree heart blockage or congestive heart failure [CHF]); severe diabetes as described below)
 - a. Predisposition to severe hypoglycemia (2 or more serious hypoglycemic episodes requiring assistance within the past year)
 - b. Any hospitalization or emergency room visit due to poor diabetic control within the past 6 months
 - c. Currently untreated diabetes mellitus or previously untreated subjects who initiated oral anti-diabetic medication or insulin within 3 months prior to Day 1
 - d. Any sign of diabetic retinopathy in either eye
 - e. Uncontrolled diabetes mellitus defined by Hemoglobin A1c $> 12\%$ taken within the last 3 months

2. Clinically significant systemic disease (e.g., severe diabetes as previously defined, myasthenia gravis, cancer, hepatic, renal, endocrine, or cardiovascular disorders) that might interfere with the study
3. Initiation of treatment with or any changes to the current dosage, drug, or regimen of any systemic adrenergic or cholinergic drugs within 7 days prior to screening or during the study ([Appendix 4](#))
4. Participation in any investigational study within 30 days prior to screening and during the study
5. Females of childbearing potential who are pregnant, nursing, planning a pregnancy, or not using a medically acceptable form of birth control. Acceptable methods include the use of at least one of the following: intrauterine device (IUD), hormonal (oral, injection, patch, implant, ring), barrier with spermicide (condom, diaphragm), or abstinence. A female is considered to be of childbearing potential unless she is 1 year postmenopausal or 3 months post-surgical sterilization. All females of childbearing potential including those with post-tubal ligation must have a negative urine pregnancy test result at Visit 1 (Screening/Baseline), Visit 2 (Treatment), and Visit 3 (Treatment) examinations and must intend to not become pregnant during the study
6. Resting HR outside the specified range (50–110 beats per minute) at Visit 1 (Screening/Baseline). HR may be repeated **only once** if outside the specified range following at least a 5-minute rest period in the sitting position
7. Hypertension with resting diastolic BP > 105 mmHg or systolic BP > 160 mmHg at Visit 1 (Screening/Baseline). BP may be repeated **only once** if outside the specified range following at least a 5-minute rest period in the sitting position

6 TREATMENT OF SUBJECTS

Approximately 160 DLD subjects ≥ 18 years of age will be randomized in a 1:1 ratio to 1 of 2 treatment arms (Nyxol or placebo), with the expectation that approximately 136 subjects will be evaluable for efficacy. Randomization will be stratified [REDACTED] [REDACTED]. There will be no treatment administered on Visit 4 (follow-up phone call).

6.1 Treatment Adherence

All subjects must be instructed on the importance of following the once-daily dosing regimen and maintaining their dosing diaries. Beginning the day of Visit 1 (Screening/Baseline; Day 1) subjects will instill one drop of study medication in the evening (at 8PM to 10PM) at or near bedtime OU. Subjects will repeat this instillation, using one bottle per day, 13 or 14 more times for a total of up to 15 doses over the course of the study. Subjects are to bring all opened bottles as well as any unopened study medication into the study site at Visit 2 and Visit 3. Treatment adherence will be measured by counting the dropper bottles at the start of the study and those remaining at each study visit. Subjects will also bring their diary to Visit 2 and Visit 3 and dosing will be reviewed by study staff.

6.2 Concomitant Medications

As noted in the exclusion criteria (Section 5.1), use of any topical prescription or OTC ophthalmic medications of any kind within 7 days of screening, with the exception of lid scrubs with OTC products (e.g., OCuSOFT® lid scrub, SteriLid®, baby shampoo, etc.), is prohibited. Many drugs, both prescription and OTC, contain active ingredients that can affect PD. This would include many eye drops, such as Visine®, that would be used to reduce redness, most cough or cold preparations, antihistamines and bronchodilators, most nose drops, most BP medications, many drugs used for migraines, and many other products.

Additionally, initiation of treatment with or any changes to the current dosage, drug, or regimen of any systemic adrenergic or cholinergic drugs (Appendix 4) within 7 days prior to screening, or during the study, is prohibited. However, a subject can be treated with a systemic adrenoceptor antagonist, for example, as long as the particular agent and its dose and regimen had been consistent for the 7 days prior to screening, and there was no reason to believe that alteration would be necessary at some point later during the study.

If there is any question about whether a medication is acceptable, the Medical Monitor should be consulted before proceeding.

Use of all medications shall be documented on the appropriate eCRF. Investigators are encouraged to contact the Medical Monitor for any questions regarding allowed medications. Judgment of continued study participation by the subject and inclusion of this subject's subsequent visits in the safety and efficacy analysis will be made by Ocuphire.

All medications taken by the subject within 30 days prior to the Screening Visit and during the study will be recorded in the eCRF. The name of the drug, dose, route of

administration, duration of treatment, and indication will be recorded for each medication. For combination products (e.g., Contac®, Cosept®), the brand name is required. For non-combination products, the generic name is desired. The use of routine ophthalmic diagnostic pharmaceutical agents (e.g., fluorescein and local anesthetic) will be allowed and should be documented. Any change in dosing parameters should also be recorded in the eCRF.

7 ASSESSMENT OF EFFICACY

7.1 Specification of the Efficacy Parameters

The primary efficacy endpoint is the percent of subjects with ≥ 15 ETDRS letters (≥ 3 lines) of improvement in the study eye compared to baseline in monocular mLCVA at Day 8.

[REDACTED]

[REDACTED] The study eye and non-study eye, as well as binocular, will be evaluated at all appropriate assessments. Secondary efficacy endpoints can be found in [Section 4.1](#).

All of the efficacy endpoints will be analyzed overall, and by light/dark irides at all timepoints. The mLCVA endpoints will be analyzed by baseline PD [REDACTED] [REDACTED] and [REDACTED] subpoint.

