4.2 Description and Schedule of Visits and Procedures

A sample size of approximately 160 DLD subjects ≥ 18 years of age will be randomized in a 1:1 ratio to 1 of 2 treatment arms (Nyxol or placebo), with the expectation that approximately 136 subjects will be evaluable for efficacy. Randomization will be stratified by iris color (light/dark irides). Study procedures are shown in detail in [Table 2](#).

Table 2 Screening, Baseline, Treatment, and Follow-Up Visits and Procedures

	Screening/Baseline [a]	Treatment	Treatment	TC Follow- Up
[REDACTED]	■	■	■	
[REDACTED]	■	■	■	
[REDACTED]	■	■	■	
[REDACTED]	■	■	■	
[REDACTED]	■	■	■	
[REDACTED]	■	■	■	
[REDACTED]	■	■	■	
[REDACTED]	■		■	
[REDACTED]	■		■	
Adverse events	X	X	X	X
Randomization number assigned	X			
Medications dispensed/Re- dispensed	X	X		
Diary dispensed/Re-dispensed	X	X		

Abbreviations: BAT, Brightness Acuity Tester; BCDVA, best-corrected distance visual acuity; CCLRU, Cornea and Contact Lens Research Unit; DCNVA, distance-corrected near visual acuity; mLcVA, mesopic low-contrast visual acuity

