9 STATISTICS

9.1 Sample Size

A sample size of approximately 136 subjects (68 per treatment group) that are evaluable for efficacy (i.e. who have a Day 8 mLcVA measurement) is needed for the study.

All subjects will be randomized into the study in a 1:1 ratio to 1 of the 2 treatment arms (Nyxol or placebo), [REDACTED]

It is assumed that there will be approximately 15% drop-out. To account for this drop-out, a total of approximately 160 subjects will be randomized into the study.

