9.3 Statistical Methods

9.3.1 General Considerations

All continuous variables will be summarized by treatment and timepoint (as applicable) using descriptive statistics (n, mean, median, standard deviation, minimum, and maximum). All categorical variables will be summarized by treatment and timepoint (as applicable) using frequency counts and percentages.

All study data will be listed by treatment, subject and timepoint (as applicable).

All statistical tests will be performed using a significance level of 5% (two-tailed). The p-values for the analysis of secondary efficacy endpoints will be considered descriptive.

9.3.2 *Demographic and Baseline Characteristics*

Demographic and baseline characteristics such as age, race, and sex will be summarized by treatment group using the mITT, PP population, ARP, and the SP. These data will also be provided in by-subject listings.

9.3.3 *Subject Disposition*

Subject disposition, including randomization, and completion and withdrawal from the study will be summarized using the ARP. These data will also be provided in by-subject listings.

9.3.4 *Medical History and Prior/Concomitant Medications*

Medical history will be coded using the latest version of Medical Dictionary for Regulatory Activities (MedDRA) and will be summarized by treatment group using the SP.

Prior medications (medications with an end date prior to the date of randomization) and concomitant medications (medications with a start or end date after the date of randomization) will be coded using World Health Organization Drug Dictionary and will both be summarized by treatment group using the SP.

Medical history and prior and concomitant medications will also be provided in by-subject listings.

9.3.5 *Analysis of Efficacy*

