9.1.2. Secondary and Exploratory Efficacy Analysis

Secondary and exploratory efficacy endpoints are indicated in [Section 4.2.2](#). Secondary and exploratory efficacy endpoints will be analyzed by study eye, non-study eye, the best of either eye, and binocular, unless otherwise indicated.

Visual acuity assessments (mLCVA, pLCVA, mHCVA, and DCNVA) will be summarized using letters. For mLCVA, pLCVA, and mHCVA, the assessments will also be summarized using logMAR units. Only letters will be recorded in the CRF. Letters will be converted to logMAR using the following formula: $\text{logMAR} = 0.02 * (\text{S} - \# \text{ Letters})$, where $\text{S} = 55$. The values of S are the number of letters read equivalent to a Snellen Acuity of 20/20. For example, for mLCVA, if the # letters = 55, then $\text{logMAR} = 0.02 * (55 - 55) = 0.00$; if # letters > 55, then logMAR is negative.

Each of the continuous secondary efficacy endpoints will be analyzed using analysis of covariance (ANCOVA), with change from baseline as the dependent variable, treatment, and [REDACTED] and the respective baseline value included as the covariate.

Each ANCOVA will be performed using the mITT and PP populations. The output from each ANCOVA will include the LSM and SE for both treatment groups, along with the placebo-corrected LSM, its 95% CI and associated p-value.

For each of the secondary endpoints related to percent of subjects achieving certain criteria, the analysis will be performed using a logistic regression model with treatment [REDACTED] [REDACTED]s, and the respective baseline as a covariate. For each analysis, the percentage of subjects in each treatment group meeting the criteria, the OR with 95% CI and p-value will be provided.

In addition, each secondary efficacy endpoint will be analyzed by [REDACTED] the same model indicated above but without irides as a factor.

For Day 8 and Day 15, the time since last dose of study treatment will be calculated as follows: date/time of visit minus date/time of the most recent dose of study medication in the subject diary. [REDACTED]

[REDACTED] For each subject, the category could be different for Day 8 and Day 15. Summaries of improvement in mLCVA, and change and percent change in pupil diameter, will be presented based on these categorizations.

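### Efficacy by iris colour is planned as separate refits within light and dark irides, and the readable text gives no direct estimate of whether the effect differs between them

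*Protocol*

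**What the plan says.** Protocol 7.1 sets the scope: "All of the efficacy endpoints will be analyzed overall, and by light/dark irides at all timepoints". That covers the primary endpoint as well as the secondary ones. The same section adds an analysis of the mLCVA endpoints by baseline pupil diameter.

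Iris colour is also the randomization stratum. Protocol 4.2: "Randomization will be stratified by iris color (light/dark irides".

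SAP 9.1.2 gives the method for secondary endpoints. Each is analysed by a factor that is redacted, with "the same model indicated above but without irides as a factor". The term would be dropped because it is constant inside one stratum, so this reads as a separate fit in each colour. The models in SAP 9.1.2 report a treatment contrast or odds ratio with a 95% CI and a p-value. SAP 9.1.1 plans subgroup analyses of the primary endpoint with the same model on observed cases; the factor there is also redacted.

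No treatment-by-irides term, test or estimate appears in the readable text of either document. Parts of Protocol 9.3.5 and SAP 7.2.2, 9.1.1 and 9.1.2 are redacted and the list of planned tables cannot be read, so this is a statement about the visible text only.

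**The concern.** Whether an effect differs between two strata is a question about the difference between two effects. Separate p-values do not answer it. Each stratum holds only part of the sample, so its power is lower than the trial's, and one p-value can easily fall below 0.05 while the other does not, even when the true effect is the same in both.

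The outputs will contain many such pairs: several endpoints, up to four eye definitions (study eye, non-study eye, best of either eye, binocular) and two post-baseline visits. A reader who sees significance in one colour only may conclude that the drop works in that colour and not in the other. What is at stake is a misleading subgroup statement in the report. The trial's main conclusion is not at risk.

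**Working it through.** **Inputs from the documents.** Two-sided 5% level (Protocol 9.3.1: "All statistical tests will be performed using a significance level of 5% (two-tailed"). Protocol 9.1 gives 136 evaluable subjects ("A sample size of approximately 136 subjects (68 per treatment group) that are evaluable for efficacy"), 1:1 allocation ("All subjects will be randomized into the study in a 1:1 ratio to 1 of the 2 treatment arms"), the drop-out assumption ("It is assumed that there will be approximately 15% drop-out") and the total ("a total of approximately 160 subjects will be randomized into the study").

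**Inputs assumed.** The power and response rates behind the 136 are not visible, nor is the expected light/dark split. I take overall power of 80-90% as the working range, with wider values for other endpoints, and splits of 50:50, 40:60, 30:70 and 20:80.

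**Step 1: the plan's own figure.** 136 / (1 - 0.15) = 160, which matches. The 136 itself cannot be re-derived.

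**Step 2: significance in exactly one colour under a uniform effect.** Let θ be the overall noncentrality. A stratum with share f has noncentrality θ√f, and the other has θ√(1-f). Power in the favourable direction is a = Φ(θ√f - 1.96) and b = Φ(θ√(1-f) - 1.96). The strata are independent, so P(exactly one significant) = a(1-b) + b(1-a).

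- 80% power: θ = 1.960 + 0.842 = 2.802. At 50:50, θ√0.5 = 1.981 and a = b = Φ(0.021) = 0.508. Result: 2 × 0.508 × 0.492 = 0.50.
- 80% power, 30:70: a = 0.335, b = 0.650. Result: 0.335 × 0.350 + 0.650 × 0.665 = 0.55.
- 90% power, 50:50: a = b = 0.630. Result: 2 × 0.630 × 0.370 = 0.47.
- 90% power, 20:80: a = 0.305, b = 0.826. Result: 0.305 × 0.174 + 0.826 × 0.695 = 0.63.

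| Overall power | 50:50 | 40:60 | 30:70 | 20:80 |
|---|---|---|---|---|
| 80% | 50% | 51% | 55% | 61% |
| 90% | 47% | 49% | 54% | 63% |

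**Step 3: outside that range.** Across the same splits the rate is 49-56% at 70% power and 40-61% at 95%. It is 41-44% at 50% power, 21-22% at 20%, and 5% with no effect. At the strong end it is 24-52% at 99% power and 10-38% at 99.9%.

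Pupil diameter illustrates a very strong endpoint. Table 1 of the protocol gives p < 0.0001 against placebo in the 39-subject study NYXG-201, so z is at least 3.89. Treating that z as the true effect and scaling it to 136 subjects gives 3.89 × √(136/39) = 7.3. The rate is then about 0.2% at 50:50 and 2% at 30:70.

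**Step 4: responder check.** With 68 per arm split into 34 per arm in each colour, assumed rates of 30% vs 10% give overall power of 84%, power per colour of 54%, and exactly one colour significant in 50% of trials. Rates of 25% vs 5% give 91%, 64% and 46%.

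**Step 5: what an interaction term would do.** Tested at 0.05, it would flag a uniform effect 5% of the time. It is also weak. At 50:50 the standard error of the difference between strata is twice that of the overall effect, so an interaction as large as the overall effect has noncentrality θ/2. Power is Φ(1.401 - 1.96) = 29% when overall power is 80%, and Φ(1.621 - 1.96) = 37% when it is 90%.

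**The case against.** The strongest reply is that most of the needed output is already planned. The subgroup runs use the same models, so each stratum's effect will come with a 95% CI. Because the strata are independent, a reader could form the difference and its interval from the two estimates. This stands. The missing piece is a direct estimate, not the underlying information.

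It also stands that little inferential weight rests on these analyses. Protocol 9.3.1 treats secondary p-values as descriptive. The fixed sequence added in SAP 9 is for the mITT population and the study eye. No visible success rule depends on an iris subgroup.

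A reader might infer more than the documents support in four ways:

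- *That about half of all iris comparisons would mislead.* The rate depends on each endpoint's power and on the split, neither of which is visible. It runs from about 5% with no effect to about 63%, and is near zero for a very strong endpoint.
- *That the plan will judge heterogeneity by comparing two p-values.* Neither document states any rule for judging it.
- *That iris colour was chosen as a stratum because response may differ by it, or that labelling by colour is at stake.* The readable text gives no reason for the stratification and does not link iris colour to labelling.
- *That no interaction analysis exists.* Redactions fall exactly where one would be specified.

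The reply does not remove the point. Calling p-values descriptive does not stop a table that shows significance in one colour only from being read as a difference.

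**Conclusion.** The point holds as a minor improvement. In the readable text, the plan for iris colour is a separate refit in each stratum without a direct estimate of the difference. For an endpoint with 80-90% overall power and a split between 50:50 and 20:80, a uniform effect would be significant in exactly one colour in about 47-63% of trials.

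That range rests on the assumed power and split, a normal approximation and a truly common effect. Endpoints, eyes and visits are correlated, so it is an average rate per comparison and not a share of independent comparisons. The consequence is confined to interpretation and leaves the primary success rule untouched.

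**What to change.** 1. For each continuous efficacy endpoint, fit one full-sample model with treatment, irides, baseline and treatment by irides. Report the interaction estimate with its 95% CI beside the stratum effects and CIs already planned.
2. For sparse responder endpoints, report the risk difference in each stratum and the difference between the two, each with a CI. Odds ratios may not be estimable here. With an assumed placebo rate of 5% and 34 placebo subjects in a stratum, the chance of no placebo responder is 0.95^34 = 17%.
3. State in the SAP that significance in one colour alone will not be read as evidence of a differential effect. Omitting the within-stratum p-values would help, but that is a reporting preference.
4. Handle baseline pupil diameter in the same way.

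The cost is a few lines of SAP text, one model term and some added table rows, with no new data, subjects or visits. The downside is that the interaction will be imprecise (29-37% power in step 5), so its estimate and CI should lead, and a non-significant interaction should not be taken as proof of a uniform effect.
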